13.6.6.3 NTDT Population

Proportion of Subjects who have an Hb Increase of ≥ 1.0 g/dL Endpoints

The number and percentage of subjects who have an Hb increase of ≥ 1.0 g/dL from Baseline for ≥ 14 days in the absence of RBC transfusions will be calculated at all post-Baseline Hb collection time points. All Hb values, including those collected at unscheduled visits but excluding values collected within 8 weeks after a RBC transfusion, will be sorted by date. For each value and the next subsequent value in time, the values and the time between values will be compared. If both values are increased ≥ 1.0 g/dL from Baseline and are ≥ 14 days apart, the subject will be counted as a yes in the proportion. The proportion of subjects who have an Hb increase of ≥ 1.0 g/dL from Baseline for ≥ 14 days, in the absence of RBC transfusions, in active arms will be compared to the placebo group using CMH tests. ORs, 95% CIs, and p-values will be reported. The difference in proportions (active arm-Placebo and the combined active arms-Placebo) and corresponding 95% CI will be also provided

The number and percentage of subjects who have an Hb increase of ≥ 1.0 g/dL from Baseline will be calculated at all post-Baseline Hb collection time points. For Week 24 and Week 36 data, the proportion of subjects with increases from Baseline of ≥ 1.0 g/dL in active arms will be compared to the placebo group using CMH tests. ORs, 95% CIs, and p-values will be reported. The difference in proportions (active arm-Placebo and the combined active arms-Placebo) and corresponding 95% CI will be also provided.

Proportion of Subjects who are RBC Transfusion-Free Over 36 Weeks Endpoint

The number and percentage of subjects who remain RBC transfusion free throughout the 36-week treatment period will be reported. Additionally, the number and percentage of subjects who have remained transfusion free since Baseline at each post-Baseline timepoint prior to Week 36 will be reported. Transfusion burden data will also be listed on the ITT Analysis Set.

Duration of the Mean Hb Increase from Baseline of ≥ 1.0 g/dL Over 36 Weeks

Duration of Hb increase from Baseline of ≥ 1.0 g/dL over 36 weeks will be summarized descriptively by treatment arm. The duration will be calculated according to the following:

1. Sort all post-baseline non-missing laboratory Hb values for a subject, including unscheduled, chronologically.
2. For any Hb change from baseline values that are ≥ 1.0 g/dL, compute the following:
 - a. Date of Hb change from baseline value ≥ 1.0 g/dL – (Date of previous non-missing laboratory Hb value)
 - b. Note: The date of the previous non-missing laboratory Hb value may include baseline values.
3. For each subject, sum up all values from #2 above.

Mean Change from Baseline in NTDT-PRO and SF-36 Quality of Life Tools

Subjects in the NTDT Population will complete two questionnaires, SF-36 and NTDT-PRO, at Baseline and Weeks 12, 24, and 36.

Similar to the TDT Population, descriptive statistics for the eight scale scores and the two component scores of the SF-36 will be tabulated at Baseline and at Weeks 12, 24, and 36. Change from Baseline to each post-Baseline assessment will also be presented for each scale and component score.

The NTDT-PRO consists of eight items. Questions 1 and 2 assess tiredness with and without physical activity. Questions 3 and 4 assess weakness with and without physical activity. Questions 5 and 6 assess shortness of breath with and without physical activity. The final two items assess the overall severity and progression of thalassemia symptoms. Items 1 – 4 are grouped into the Tiredness/Weakness Domain and Items 5 – 6 are grouped into the Shortness of Breath Domain.

Scores for the 6 domain related questions range from 0 (no tiredness/weakness/shortness of breath) to 10 (extreme tiredness/weakness/shortness of breath).

The Tiredness/Weakness domain score will be calculated by averaging the responses to questions 1-4. The Shortness of Breath domain score will be calculated by averaging the responses to questions 5-6. If any responses are missing in questions 1-4 or 5-6 for the timepoint of evaluation, then the Tiredness/Weakness and Shortness of Breath domain scores cannot be calculated, respectively.

The total score will be calculated by averaging the responses to questions 1-6. If any responses are missing at the time point in question, then the total score cannot be calculated.

Descriptive statistics of the Tiredness/Weakness and Shortness of Breath domain scores and total score, and changes from Baseline, will be reported at Baseline and at Weeks 12, 24, and 36 by treatment group, as well as changes from the last assessment, i.e., from Week 12 to Week 24 and Week 24 to Week 36.

The mean change from Baseline in the NTDT-PRO total score will be assessed using an ANCOVA model with Baseline value as a covariate. Summary statistics for observed values at Baseline and Week 24 and change from Baseline to Week 24 will be presented. LSMean estimates and 95% CIs will be presented for each active arm and placebo at Week 24. The LSMean difference estimates and associated 95% CIs and p-values at Week 24 will also be reported for each active arm compared to placebo and the combined active arms-Placebo. The Week 36 NTDT-PRO total score will be analyzed with a similar model, as will the NTDT-PRO T/W and SOB domain scores at Weeks 24 and 36.

By-subject listings of SF-36 data and NTDT-PRO data will be presented on the ITT Analysis Set.

Proportion of Subjects with an Increase from Baseline of $\geq 3\%$ in Mean HbF Over 12 Week Rolling Time Periods Endpoint

The proportion of subjects with increase from Baseline of $\geq 3\%$ in mean HbF values measured over 12-week intervals (from Day 2 to 85, Day 3 to 86, etc. through Day 170 to Day 253 (Week 36)) will be assessed using a CMH test. The number and percentage of responders and non-responders at each of the rolling time periods will be presented for each treatment group as well as ORs, 95% CIs, and p-values from the CMH tests. The difference in proportions (active arm-Placebo and the combined active arms-Placebo) and corresponding 95% CI will be also provided. Bar plots will be provided. The proportion of subjects with response in HbF, where a responder has an increase of $\geq 3\%$ at each of the rolling time periods compared to Baseline, Odds ratios, 95% CI, and p values will be displayed by treatment arm.

Proportion of Subjects with an Increase from Baseline of ≥ 1.0 g/dL in Mean Hb Over 12 Week Rolling Time Periods Endpoint

The proportion of subjects with increase from Baseline of ≥ 1.0 g/dL in mean Hb values measured over 12 week intervals (from Day 2 to 85, Day 3 to 86, etc. through Day 170 to Day 253 (Week 36)) will be evaluated using a Cochran-Mantel-Haenzel (CMH) test to compare the proportion of subjects who achieved improvement between the placebo group and each of the 2 active treatment arms (IMR-687 lower dose and IMR-687 higher dose) and the combined active arms. The number and percentage of responders and non-responders, ORs, 95% CIs, p-values from the CMH tests and the difference in proportions and corresponding 95% CI will be provided similarly to the HbF above.

Time to First Hb Increase (≥ 1.0 g/dL)

The time to first Hb increase will be analyzed using Kaplan-Meier methods. Time in months to the first Hb increase can be calculated as $([\text{date of first Hb increase} - \text{date of first dose} + 1] / 30.4375)$.

Subjects who experience no Hb increase during the study will be censored at their study end date (or data cut-off date if the study end date is not available). The number and percentage of subjects with events (subjects who experienced at least 1 Hb increase on-study) and censored (subjects who did not experience any Hb increase on-study) will be presented. The 25th, 50th (median), and 75th percentiles, along with associated 2-sided 95% CIs based on the Brookmeyer and Crowley method will be presented. The p-values from a log rank test and hazard ratios (and 95% CIs) estimated from a Cox regression

model will be presented for comparison of each treatment arm to placebo. Kaplan-Meier figures will be produced for the time to first Hb increase with separate curves for each treatment arm.

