Proportion of subjects who have an Hb increase of ≥ 1.0 g/dL from Baseline for ≥ 14 days in the absence of RBC transfusions	Any consecutive 14-day period through Week 36	CMH analysis: Odds ratios (active arm vs. placebo), 95% CI, p-value, difference in proportions (active arm-Placebo) and corresponding 95% CI will be provided

Proportion of subjects who have an increase from Baseline of ≥ 1.0 g/dL in Hb in the absence of transfusions	Week 24, Week 36	Descriptive Summary
Proportion of subjects who have an increase from Baseline of ≥ 1.5 g/dL in Hb in the absence of transfusions	Week 24, and Week 36	Descriptive Summary
Duration of the Hb increase from Baseline of ≥ 1.0 g/dL over 36 weeks	Over 36 weeks from Baseline	Descriptive Summary
Mean change from Baseline in NTDT-PRO total score and domain scores including T/W and SOB domain scores over a continuous 12-week interval	Week 12 to Week 24, and Week 24 to Week 36.	Descriptive Summary
Mean change from Baseline in NTDT-PRO total score and domain scores including T/W and SOB domain scores	Week 24, Week 36	Analysis of Covariance (ANCOVA) analysis with Baseline value as a covariate: LSMean (95% CI), LSMean difference (95% CI) between each active dose and placebo, and p-value.
Rolling 12-week analysis for Proportion of subjects with an increase in Hb	Rolling time periods – Day 2 to 85, Day 3 to 86, etc. through Day 170 to Day 253 (Week 36)	
 • Cochran-Mantel Haenszel (CMH) analysis: Odds ratios (OR) (active arms vs. placebo), 2-sided 95% CI, p-value • Summary of number and percentage of responders with difference in proportions (active arm-Placebo) and corresponding 2-sided 95% CI • Forest plots of ORs, 2-sided 95% CIs, p-value – Higher dose vs. placebo, Lower dose vs. placebo
Time to first Hb increase (≥ 1.0 g/dL)	Over 36 weeks from Baseline	
 • Kaplan-Meier methods - log rank test and hazard ratios (and 95% CIs) will be estimated from a Cox regression model • Kaplan-Meier for the time to first Hb increase with separate curves for each treatment arm

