13.6.6.2 Imputation Methods for the Hb Endpoints for the NTDT Population

The following imputation rules will be applied for the exploratory efficacy endpoints related to Hb (Proportion of subjects who have an Hb increase of ≥ 1.0 g/dL from Baseline for ≥ 14 days in the absence of RBC transfusions, Number of subjects with increase from Baseline of 1.0 g/dL in mean Hb values at Week 24 and Week 36 compared to Baseline in the absence of transfusions, Duration of the mean Hb increase from Baseline of ≥ 1.0 g/dL over 36 weeks, and Proportion of subjects who have an increase from Baseline of ≥ 1.5 g/dL in mean of Hb values in the absence of transfusions):

1. For the number of subjects with increase from Baseline of 1.0 g/dL in mean Hb values at Week 24 and Week 36 compared to Baseline in the absence of transfusions endpoint, and the proportion of subjects who have an increase from Baseline of ≥ 1.5 g/dL in mean of Hb values in the absence of transfusions endpoints, subjects will be treated as non-responders for the Week 24 or Week 36 time point if they received an RBC Transfusion within the prior 8 weeks for that time point (Weeks 16-24 for the Week 24 time point, Weeks 28-36 for the Week 36 time point). For the duration of the mean Hb increase from Baseline of ≥ 1.0 g/dL over 36 weeks endpoint, an 8 week period following any transfusion will be excluded from the duration total. For the number of subjects and the proportion of subjects with an increase from Baseline endpoints, this means that the subject will not be included in the number or proportion of subjects with an increase.
2. If the subject received an RBC Transfusion during the time periods described above the Hb will be imputed as the last assessment prior to transfusion
3. If some of the Hb values are missing during any of the time periods, the duration of the non-missing values during that time period will be used for the duration of the mean increase from Baseline endpoint and the non-missing values during that time period will be used for the determination of the number or proportion of subjects with an increase from Baseline endpoints.

The number of subjects with imputed values for the exploratory efficacy endpoints and the reason for imputation will also be summarized.

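### Time to first Hb increase in NTDT has no transfusion rule, so a rise that follows an RBC transfusion counts as a favourable event

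*SAP*

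**What the plan says.** SAP 13.6.6.3 states: "The time to first Hb increase will be analyzed using Kaplan-Meier methods". The event is the first Hb rise of at least 1.0 g/dL. On censoring it says: "Subjects who experience no Hb increase during the study will be censored at their study end date", or at the data cut-off if that date is unavailable. Each arm is compared with placebo: "The p-values from a log rank test and hazard ratios (and 95% CIs) estimated from a Cox regression" model are to be presented. There is no transfusion condition. The entries for this endpoint in SAP 6.1, 9.0 and Table 12 have none either.

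SAP 13.6.6.2 opens: "The following imputation rules will be applied for the exploratory efficacy endpoints related to Hb". It then names four endpoints: at least 14 days, Week 24/36, duration, and the 1.5 g/dL responder endpoint. Time to first Hb increase is not among them.

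Elsewhere the SAP does deal with post-transfusion Hb:

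- **Mean Hb (13.6.4.2, 13.6.4.3):** a transfusion during the interval or the 8 weeks before it makes the subject a non-responder, and values within 8 weeks after a transfusion are left out of the interval mean.
- **Week 24/36 responders (13.6.6.2):** a transfusion in the preceding 8 weeks makes the subject a non-responder.
- **Duration (13.6.6.2):** "an 8 week period following any transfusion will be excluded from the duration total".
- **At least 14 days (13.6.6.3):** all Hb values are used, "including those collected at unscheduled visits but excluding values collected within 8 weeks after a RBC transfusion".

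**The concern.** In NTDT the SAP otherwise treats transfusion as invalidating a response. Here, a programmer who follows the text would score a single laboratory value lifted by donor blood as the favourable event, with no confirmation required. The between-arm comparison would then mix drug response with transfusion practice, yet it is reported with a log-rank p-value, a hazard ratio and Kaplan-Meier curves.

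On-study transfusion is possible in this population. Protocol 8.1 admits NTDT subjects with up to 3 units in the previous 12 weeks, and remaining transfusion-free over 36 weeks is itself an exploratory endpoint. The protocol also distrusts such values at entry: inclusion criterion 10 discards Hb within 21 days of a transfusion.

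**Working it through.** **Text check.** No general rule fills the gap. SAP 10.1.1 defaults to no imputation, and Appendix 3 has no rule on post-transfusion Hb. The 8-week exclusions listed above each belong to another derivation. Two further Hb outputs in 13.6.6.3 also state no exclusion of their own: the rolling 12-week proportion with a mean rise of at least 1.0 g/dL, and the proportion with that rise at every post-Baseline Hb time point. 13.6.6.2 covers only the Week 24 and Week 36 readings of the latter. The rolling endpoint, being a mean, might inherit the 13.6.4.3 rule, but this is not stated.

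**Inputs for size.** The documents give no event rate, power or hazard ratio for this endpoint, and no NTDT on-study transfusion rate, so there is no plan figure to reproduce. All of the following are assumptions:

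- True response of 10% placebo and 50% active. These figures are borrowed from SAP 8.1.2, where they refer to mean Hb over a 12-week interval.
- Transfusion of 20% (placebo) and 10% (active) among non-responders.
- A proportion q of transfusions that yields a recorded value at least 1.0 g/dL above Baseline.

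**Main illustration.** Event probability = response + q × transfusion × (1 − response). With proportional hazards, HR = ln(1 − active) / ln(1 − placebo).

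| q | Placebo events | Active events | HR |
|---|---|---|---|
| 0 | 0.10 | 0.50 | ln 0.50 / ln 0.90 = 6.6 |
| 0.25 | 0.10 + 0.25×0.20×0.90 = 0.145 | 0.50 + 0.25×0.10×0.50 = 0.5125 | ln 0.4875 / ln 0.855 = 4.6 |
| 0.5 | 0.10 + 0.5×0.20×0.90 = 0.19 | 0.50 + 0.5×0.10×0.50 = 0.525 | ln 0.475 / ln 0.81 = 3.5 |
| 1 | 0.10 + 0.20×0.90 = 0.28 | 0.50 + 0.10×0.50 = 0.55 | ln 0.45 / ln 0.72 = 2.4 |

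**Other scenarios.** These use constant hazards, with H(p) = −ln(1 − p) and HR = [H(response, active) + q·H(transfusion, active)] / [H(response, placebo) + q·H(transfusion, placebo)]. For the scenario above this version gives 4.46, 3.44 and 2.43, close to the table. Results are for q = 0.25, 0.5 and 1.

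- No drug effect, transfusion 30% placebo, 10% active: HR 0.68, 0.56, 0.46.
- No drug effect, transfusion 10% placebo, 30% active: HR 1.48, 1.80, 2.19.
- No drug effect, equal transfusion: HR 1.0.
- Response 10% versus 50%, equal 10% transfusion: HR 5.46, 4.72, 3.79, against a true 6.58.
- Response 10% versus 50%, transfusion 10% placebo, 30% active: HR 5.94, 5.51, 4.98.

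The formula explains the pattern. The recorded HR lies between the response HR and the transfusion HR. Without a drug effect, the arm transfused more looks better. With a strong effect, the HR is diluted even when active is transfused more, because the transfusion HR there, H(0.30)/H(0.10) = 3.4, is still below 6.58.

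**Effect of an 8-week exclusion.** A simulation of 4,000 trials used 30 active and 15 placebo subjects (SAP 8.1.2), Hb visits at Weeks 1, 4, 8 and so on to 36, a two-sided 0.05 log-rank test, q = 0.8 and a 4-week transfusion rise. Subjects stayed at risk after transfusion.

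| Scenario | As the SAP reads | With 8-week exclusion |
|---|---|---|
| No effect, transfusion 30% placebo / 10% active: false placebo-better result | 22% | 3% |
| No effect, transfusion 10% / 30%: false drug-better result | 15% | 0.4% |
| Response 10% v 50%, transfusion 30% / 10%: power | 27% | 80% |
| Response 10% v 50%, transfusion 10% / 10%: power | 67% | 79% |

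The simulation makes transfusion independent of drug response, which is a simplification.

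**The case against.** The strongest reply is that little hangs on this. The endpoint was added in the SAP, is exploratory and unadjusted, does not appear among the key NTDT outputs in SAP Table 4, and supports no power statement or decision rule. The secondary mean-Hb endpoints already handle transfusion. That stands, and it limits the priority.

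It is also fair that few transfusions may matter. NTDT entry bars a regular transfusion programme and requires at least 4 transfusion-free weeks. Hb is drawn about every 4 weeks after Week 4, and a transfusion given after a fall need not take Hb 1.0 g/dL above Baseline. This is why the proportion captured is varied from 25% to 100%. It makes the size uncertain; it does not supply the missing rule.

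Three stronger readings are tempting, and the documents do not support them. A reader might infer that this is the only unprotected Hb endpoint; the rolling and by-visit proportions also state no exclusion. A reader might infer a bias against IMR-687; that needs placebo to be transfused more, or a real effect to be diluted, and nothing in the documents says which arm will be transfused more. A reader might take a fall from 6.6 to 2.4 as the expected loss; it assumes every transfusion is captured, and the 10% and 50% rates belong to a different endpoint. A first crossing by any single value is an easier criterion than a 12-week mean.

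**Conclusion.** The concern holds as a gap in one exploratory endpoint. Read literally, the SAP counts a transfusion-driven Hb rise as a response and carries it into a log-rank test and a Cox hazard ratio. That conflicts with how the SAP treats its main Hb endpoints. The distortion can run either way when the drug has no effect, and it dilutes a real effect even under equal transfusion. The illustrated fall from 6.6 to between 4.6 and 2.4 rests wholly on assumed response, transfusion and capture rates. It shows that the effect can be material, not how large it will be. The secondary Hb results are not affected.

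**What to change.** In SAP 13.6.6.3, state that an Hb value collected within 8 weeks after any RBC transfusion cannot count as the first increase, and that the subject otherwise remains at risk and is censored as now. State the same exclusion for the rolling 12-week and by-visit Hb proportions.

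Adding the endpoint to the 13.6.6.2 list alone would not settle it: the first rule there is specific to other endpoints, and the second substitutes the last pre-transfusion Hb.

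Transfusion before the first increase may be treated as a competing event in a sensitivity analysis. Simple censoring at transfusion should not be the main rule. Subjects who are transfused probably differ in their chance of a later rise, so that censoring is likely informative.

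The cost is a few sentences and a derivation from transfusion dates that are already collected. Each transfusion removes roughly two scheduled Hb visits (8 weeks / 4 weeks), so there will be slightly fewer events and some will be dated later.

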### **8.4. Guidelines for Withdrawal of Subjects from Study Participation**

Subjects will be informed that they can discontinue their participation in the study at any time and for any reason.

The investigator may also remove a subject from the study at their discretion if, in the investigator's opinion, it is not in the best interest of the subject to continue in the study.

If a subject must be discontinued from study participation, the medical monitor should be informed and consulted regarding possible appropriate assessments to be completed in advance of study discontinuation. In case of discontinuation from the study, every effort will be made to complete the early termination visit assessments, if possible. If a subject does not complete the early termination assessments, then every effort should be made to obtain end of study assessments. If a final visit is not feasible, every effort to collect follow-up medical records will be attempted.

In the case of subjects who are lost to follow-up, the study site must attempt to contact the subject by phone, making at least 3 documented attempts, each at least one week apart.

Additionally, one registered letter must have been sent with a copy on file. The study site should only deem the subject as lost to follow-up no less than 30 days following the first documented phone call attempt, unless circumstances preclude this (e.g., phone service has been discontinued or there is other evidence that contact is not feasible).

If the subject discontinues the study, the specific circumstances surrounding the discontinuation must be recorded in the subject's eCRF.

Refer to Section 7 for details about randomization and treatment assignments. All data collected prior to discontinuation must be recorded in the subject's eCRF.

Justifiable reasons to discontinue a subject from treatment (Section 8.5) and/or from the study may include, but are not limited to the following:

- The subject was erroneously included in the study (i.e., did not meet eligibility criteria)
- The subject experiences an SAE assessed as possibly or probably related to study drug
- The subject is unable to comply with the requirements of the protocol
- The subject participates in another investigational study
- The subject withdraws consent to participate in the study
- A subject for whom the blind is intentionally or accidentally broken

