Week 12 (Day 84 ± 7)	54 to 106
Week 18 (Day 126 ± 7)	107 to 148
Week 24 (Day 168 ± 7)	149 to 211
Week 36 (Day 252 ± 7)	≥212
QoL	
Scheduled Study Visit (Protocol Scheduled Day)	Analysis Visit Window (Study Day)
Baseline	≤ 1
Week 12 (Day 84 ± 5)	2 to 127
Week 24 (Day 168 ± 7)	128 to 211
Week 36 (Day 252 ± 7)	≥212

Table 2: Visit Windows for Efficacy and Safety Analyses – NTDT Population

Safety Analyses – Vital Signs, Weight, 12-Lead ECG, Hematology (Except Specialty Hematology) and Chemistry	
Scheduled Study Visit (Protocol Scheduled Day)	Analysis Visit Window (Study Day)
Baseline	≤ 1
Week 1 (Day 7 ± 2)	2 to 18
Week 4 (Day 28 ± 5)	19 to 43
Week 8 (Day 56 ± 7)	44 to 71
Week 12 (Day 84 ± 7)	72 to 99
Week 16 (Day 112 ± 7)	100 to 127
Week 20 (Day 140 ± 7)	128 to 155
Week 24 (Day 168 ± 7)	156 to 183
Week 28 (Day 196 ± 7)	184 to 211
Week 32 (Day 224 ± 7)	212 to 239
Week 36 (Day 252 ± 7)	240 to 267
Week 40 (Day 280 ± 7)	≥ 268
Safety Analyses – Urinalysis	
Scheduled Study Visit (Protocol Scheduled Day)	Analysis Visit Window (Study Day)
Baseline	≤ 1
Week 4 (Day 28 ± 5)	2 to 57
Week 12 (Day 84 ± 7)	58 to 127
Week 24 (Day 168 ± 7)	128 to 211
Week 36 (Day 252 ± 7)	≥212
Safety Analyses – Coagulation	
Scheduled Study Visit (Protocol Scheduled Day)	Analysis Visit Window (Study Day)
Baseline	≤ 1
Week 12 (Day 84 ± 7)	2 to 127
Week 24 (Day 168 ± 7)	128 to 211
Week 36 (Day 252 ± 7)	≥212
Efficacy Analyses – Specialty Hematology	
Scheduled Study Visit (Protocol Scheduled Day)	Analysis Visit Window (Study Day)
Baseline	≤ 1
Week 4 (Day 28 ± 5)	2 to 57

Week 12 (Day 84 ± 7)	58 to 127
Week 24 (Day 168 ± 7)	128 to 211
Week 36 (Day 252 ± 7)	≥212
Efficacy Analyses- PD Biomarkers	
Scheduled Study Visit (Protocol Scheduled Day)	Analysis Visit Window (Study Day)
Baseline	≤ 1
Week 4 (Day 28 ± 5)	2 to 57
Week 12 (Day 84 ± 7)	58 to 127
Week 24 (Day 168 ± 7)	128 to 211
Week 36 (Day 252 ± 7)	≥212
QoL	
Scheduled Study Visit (Protocol Scheduled Day)	Analysis Visit Window (Study Day)
Baseline	≤ 1
Week 12 (Day 84 ± 5)	2 to 127
Week 24 (Day 168 ± 7)	128 to 211
Week 36 (Day 252 ± 7)	≥212

Windowing will be applied prior to any missing data calculations. The last non-missing measurement taken prior to the date of first dose (including unscheduled assessments) will be labeled as “Baseline”. Screening visits that occurred before the Baseline visit will not be assigned an analysis visit. The early discontinuation visit will be eligible for allocation to an analysis visit.

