Appendix 2 Schedule of Assessments – NTDT Population

	Screening	Baseline	Double-blind, Placebo-controlled Treatment											EOT ^a / ET	End of Study (Safety FU)
Visit number	1	2	3	4	5	6	7	8	9	10	11	12	13	14	
Study Week(s)	-4 to 0	NA	1	2	4	8	12	16	20	24	28	32	36	40	
Study Day(s)	-28 to -1	1^b	7±2	14±2	28±5	56±7	84±7	112±7	140±7	168±7	196±7	224±7	252±7	280±7	
On-site visits	X	X	X		X	X	X	X	X	X	X	X	X	X	
Telephone visits ^c				X											
Informed consent	X														
PGx ICF and blood draw (optional) ^d	X														
Demographic information	X														
Medical/disease history ^e	X														
Inclusion/exclusion criteria	X	X													
ECOG score	X														
Clinically indicated virology (Hep A, B, and C and HIV)	X														
Historical transfusion burden ^f	X	X													
Randomization		X													
Vital signs ^g	X	X	X		X	X	X	X	X	X	X	X	X	X	
Weight	X	X	X		X	X	X	X	X	X	X	X	X	X	
Height	X														
Transfusion burden ^h					X	X	X	X	X	X	X	X	X	X	

	Screening	Baseline	Double-blind, Placebo-controlled Treatment										EOT ^a / ET	End of Study (Safety FU)
Visit number	1	2	3	4	5	6	7	8	9	10	11	12	13	14
Study Week(s)	-4 to 0	NA	1	2	4	8	12	16	20	24	28	32	36	40
Study Day(s)	-28 to -1	1 ^b	7±2	14±2	28±5	56±7	84±7	112±7	140±7	168±7	196±7	224±7	252±7	280±7
Physical examination ⁱ	X	X	X		X	X	X	X	X	X	X	X	X	X
12-Lead ECG ^j	X	X	X		X	X	X	X	X	X	X	X	X	X
Hematology and chemistry	X	X	X		X	X	X	X	X	X	X	X	X	X
Coagulation studies	X					X			X				X	
Urinalysis	X	X			X		X			X			X	
Pregnancy testing ^k	X	X	X		X	X	X	X	X	X	X	X	X	X
Specialty hematology ^l	X	X			X		X			X			X	
PD markers ^m	X	X			X		X			X			X	
IMR-687 plasma PK ⁿ		X	X		X					X			X	
QOL assessments ^o		X				X			X				X	
Study drug admin at site ^p		X	X		X	X	X	X	X	X	X	X	X	
Study drug dispensing		X			X	X	X	X	X	X	X	X		
Study drug admin		Oral administration of IMR-687 or placebo qd												
AEs and concomitant medications		Continuous ^q												

AEs = adverse events; ECG = electrocardiogram; ECOG = Eastern Cooperative Oncology Group; ET = early termination; EOT = end of treatment; FU = follow-up; Hb = hemoglobin; HIV = human immunodeficiency virus; hsCRP = highly sensitive C-reactive protein; ICAM-1 = intercellular adhesion molecule 1; ICF = informed consent form; NTDT-PRO = non- -thalassemia patient reported outcome; NT-proBNP = N-terminal pro B-type natriuretic peptide; PD = pharmacodynamics; PE = physical

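### Time to first Hb increase (NTDT, exploratory) is censored at study end rather than at the last Hb, and lets an off-drug Week 40 value count: a small bias and a 36/40-week conflict that one sentence can remove

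*SAP*

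**What the plan says.** SAP 13.6.6.3 (Time to First Hb Increase) gives the censoring rule: "Subjects who experience no Hb increase during the study will be censored at their study end date", or the "or data cut-off date if the study end date is not available". It does not mention the last Hb assessment, and neither that section nor Appendix 3 defines the study end date. The censored times feed Kaplan-Meier curves and percentiles, and a comparison of each arm with placebo: "The p-values from a log rank test and hazard ratios (and 95% CIs) estimated from a Cox regression" model.

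SAP Table 12 gives the time frame as "Over 36 weeks from Baseline". Section 13.6.6.3 instead counts any increase during the study.

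In SAP Appendix 2 the row "Hematology and chemistry" is marked at Weeks 1, 4 and 8, then every 4 weeks to Week 36, and again at Week 40. SAP Table 2, under "Vital Signs, Weight, 12-Lead ECG, Hematology (Except Specialty Hematology) and Chemistry", gives Week 40 its own window from Day 268. The last dose is taken at Week 36.

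Protocol 8.4 allows a site to declare a subject lost "no less than 30 days following the first documented phone call attempt", unless circumstances preclude this.

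**The concern.** A subject belongs in the risk set only while an event could be observed. Here that means up to the last Hb draw. If the censoring date falls later, the subject stays in the denominator at visits where an increase could not have been recorded. The estimated event rate is then too low and the percentiles too late. If this happens more in one arm, the log-rank test and hazard ratio move as well.

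The second issue does not depend on dropout. A completer with no rise by Week 36 but a rise at Week 40, four weeks after the last dose, is an event under the text of 13.6.6.3 and lies outside the time frame in Table 12. Two programmers could reasonably code this differently.

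**Working it through.** The documents state no event count, hazard ratio or power for this endpoint, so there is no figure to reproduce. The check asks who can have a gap between last Hb and censoring, and what the gap does.

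**Inputs**
- Hb draws on nominal Days 7, 28, 56, then every 28 days to 252, and Day 280 (Protocol Table 3, SAP Appendix 2).
- The early termination visit repeats the Week 36 procedures, which include hematology (SAP Appendix 2, note a).
- Subjects who stop study drug must leave the study (Protocol 8.5.1).
- Arm sizes of 30 active and 15 placebo, and response of 50% versus 10% (SAP 8.1.2). Rates of 30% versus 30% and 50% versus 20% are added as assumptions.
- Dropout is not stated, so 0–40% was assumed. The nearest figure is the cap on replacements, 10 of about 60, or 17% (Protocol 8.6).
- Gap length is not stated. Assumed: 28 days to the missed visit + 30 days from the first call = 58 days.

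**Who has a gap.** A completer's study end is the Week 40 visit, where Hb is drawn, so the gap is 0. A subject whose early termination Hb is at study end also has a gap of 0. A gap arises for subjects who leave without a final Hb and for subjects still ongoing at a data cut-off.

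**Mechanism.** Take a subject last seen on Day 84. With a 58-day gap, censoring falls on Day 84 + 58 = 142, so the subject is counted at risk on Days 112 and 140 although no Hb was drawn. If R subjects in an arm can show an event at a visit and L cannot but are still counted, the estimated hazard is d/(R + L) = h × R/(R + L), where d is the number of events and h = d/R. The arm's curve is too low whenever L > 0. The hazard ratio changes materially only if R/(R + L) differs between arms.

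**Large-sample simulation** (3,000 placebo, 6,000 active, 30 replicates). Event times were exponential and detected at the next draw, with a Cox model using Efron ties. Loss is the probability of leaving by Day 280; gaps are in days. The ratio is HR(study-end censoring)/HR(last-Hb censoring). KM is the active-arm event rate at Day 252, last-Hb rule → study-end rule.

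| Loss, placebo/active | Gap | HR ratio, 10% vs 50% | HR ratio, 30% vs 30% | KM, true 50% | KM, true 30% |
|---|---|---|---|---|---|
| none | – | 1.000 | 1.000 | 50.0 → 50.0 | 29.8 → 29.8 |
| 15%/15% | 0 | 1.000 | 1.000 | 50.0 → 50.0 | 30.0 → 30.0 |
| 15%/15% | 58 | 0.998 | 1.000 | 49.9 → 48.8 | 29.9 → 29.2 |
| 30%/30% | 58 | 0.996 | 1.000 | 50.0 → 47.6 | 30.0 → 28.3 |
| 10%/25% | 58 | 0.963 | 0.966 | 50.0 → 48.0 | 30.2 → 28.8 |
| 10%/40% | 58 | 0.921 | 0.925 | 50.0 → 46.5 | 30.0 → 27.6 |
| 15%/15% | 0 placebo, 58 active | 0.968 | 0.969 | 50.0 → 48.9 | 29.9 → 29.1 |

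With equal loss the event rate falls by 0.7–1.1 points at 15% and 1.7–2.4 points at 30%.

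**Trial-size simulation** (15 versus 30, response 20% versus 50%, 58-day gap). The mean shift in log HR is −0.0002 at 17%/17% loss, −0.037 at 10%/25% and −0.080 at 10%/40%. The standard deviation of log HR is about 0.65. The two larger shifts are therefore 0.037/0.65 = 0.06 and 0.080/0.65 = 0.12 of one standard deviation.

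**The case against.** The strongest reply is that the rule rarely bites. Hb is scheduled at Week 40 and at early termination. Stopping drug means leaving the study, so no long follow-up without Hb is planned. Protocol 8.4 asks for every effort to complete a final visit. The lead analysis uses the Per Protocol set, which removes subjects who discontinue before Week 12 for reasons other than adverse events. The endpoint is exploratory, has no multiplicity-controlled claim, and is not among the outputs of SAP Table 4, although outputs may be added on request. All of this stands and limits the size.

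It could also be said that the study end date might be taken as the last visit. The SAP does not say so. The nearest term in Appendix 3, the last study participation date, is the latest of several dates, including completion or discontinuation, and can fall after the last Hb. By the same token, Protocol 8.4 does not say that the date a subject is deemed lost becomes the study end date, so 58 days is an assumption and not a documented gap.

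A third reply is that Table 12 already limits the endpoint to 36 weeks. But the operative text counts increases during the study and censors at its end, so the two places need to be reconciled.

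**Conclusion.** The censoring rule is mis-specified for subjects who leave without a final Hb. Its most predictable effect is a slightly low Kaplan-Meier event rate: about 1–2 points at 15–30% such loss. The hazard ratio moves by under 0.5% with equal loss, about 3.5% at 10% versus 25%, and about 8% at 10% versus 40%. If loss is equal but only one arm has the 58-day gap, it moves by about 3%. All of these figures rest on assumed dropout and an assumed 58-day gap, and they are small against sampling error at 15 versus 30 subjects. The Week 36/Week 40 conflict stands on the text alone.

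A reader might infer that the rule by itself biases the hazard ratio. The documents do not support that, because most subjects have no gap and a similar understatement in both arms largely cancels. A reader might also reach larger effects by assuming 20% loss in one arm and none in the other (hazard factor 0.95), or a 200-day gap from the cut-off fallback (0.86). The documents give no dropout rate or difference between arms. The fallback applies only when the study end date is missing, and an ongoing subject who attends visits would normally have had an Hb within about one 4-week interval.

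Severity: minor.

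**What to change.** Replace the censoring sentence in SAP 13.6.6.3 with:

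*Subjects without an Hb increase on or before the Week 36 (or early termination) visit are censored at the date of their last non-missing Hb on or before that visit, or at Day 1 if there is no post-baseline Hb; later Hb values are not used.*

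Delete the study-end and data cut-off wording. For a subject lost before either visit, the censoring date is then the last Hb drawn. This removes the unobservable time, covers subjects with no post-baseline value, and brings the text into line with the 36 weeks in Table 12.

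While editing, state whether the 8-week post-transfusion exclusion used for other NTDT Hb endpoints applies here. SAP 13.6.6.2 does not list this endpoint, and such an exclusion would create a further period in which no event can be seen.

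The cost is one SAP sentence and one line of programming. No data collection changes.
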